#### 3.3 Secondary objectives and endpoints

The secondary objectives are:

1) To generate an anatomically correct model of the upper respiratory tract that includes the sinus cavities (maxillary, frontal, ethmoidal, sphenoidal) and that could be used for *in vitro* optimisation study of sinus delivery formulation in the future.

It is expected to obtain from all participants a high-resolution CT scan of their head at the first initial visit that includes sinus structure allowing for realistic *in vitro* simulation and optimization for sinus delivery in the future.

2) To assess the clearance of the radio-labelled saline over 1 hour (at 0, 20 and 60 minutes post-administration) after its administration with the NMN prototype at four different pulse frequencies.

### 3.4 Data analysis and interpretation

Defined volume of radiolabelled saline (2 ml) will be delivered using the NMN device through the nasal airways with four different pulse frequency settings in front of a single-head gamma camera using the NMN device to capture a planar images. Subsequently, serial images (2 frames per second) will be recorded from the anterior and lateral view using the SPECT/CT. This allows dynamic studies of filling and emptying of the nose, including the sinuses.

#### Image analysis

The CT scan image will be reconstructed to provide transaxial image using standard protocol and the deposition, retention and clearance evaluated. The image data will be assessed quantitatively (to meet primary objective and endpoint). In addition, high resolution CT-scan of their head at the first initial visit to generate an anatomically correct model of the upper respiratory tract that includes the sinus cavities (maxillary, frontal, ethmoidal, sphenoidal) (Secondary objective and endpoints)

#### Interpretation and assumption of quantitative data

The quantitative assessment of nasal deposition, retention and clearance will be determined as a percentage of total nasal deposition (quantified using the first planar image immediately after inhalation of the radioaerosol) as a function of intensity within defined areas of the nasal cavity, left and right of the maxillary, frontal, ethmoidal and sphenoidal sinuses using standard protocol as briefly described below. Count rates in the selected region of interests will be analysed using the MATLAB Software or ImageJ Software packages (<http://rsb.info.nih.gov/ij/>). Count rates will be corrected for background activity and radioactive decay.

For analysis of the distribution of the radiolabelled saline into the different compartments, all serial images will be superimposed with regions of interest (ROI) of the nasal airways and sinuses defined as shown in Figures 6 and 7. The activity is obtained in these ROIs.

[figure not shown]

Figure 6. Regions of interest of the nasal cavity of the right and left maxillary and frontal sinuses (MR, FR, FL and ML). Image was taken from [9].

The primary endpoint of this study is the total area of distribution ( $\text{mm}^2$ ) of radiolabelled saline immediately after administration by the NMM ( $T_0$ ). This will be evaluated for each of subsites (surgically expanded ostia of the paranasal sinuses and oropharynx) and compared between treatments (A-D) which correspond to the different pulse frequencies tested. Between-treatment differences in total area of deposition of radiolabelled saline at each subsite will be compared by means of one-way analysis of variance (ANOVA) with application method as a factor.

Pairwise comparisons will be performed between each of the pulsed application methods and the continuous application (no pulse). Pairwise comparisons will be tested using a two-tailed p-value of  $<0.05$ .

Clearance will be calculated by the decrement in total radiolabelled saline between  $T_0$ ,  $T_{20}$  and  $T_{60}$ . Clearance will be evaluated for each subsite and compared between treatments (A-D). As with the primary efficacy endpoint, between-treatment differences in radiolabelled clearance will be tested by means of one-way analysis of variance (ANOVA) with application method as a factor. Pair-wise comparisons will be made between each of the pulsed application methods and the continuous application (no pulse).

The retention of radiolabelled saline will be evaluated as the Area Under the Curve between  $T_0$  and  $T_{60}$  ( $\text{AUC}_{0-60}$ ) of the following assessments:

- the total area of deposition of radiolabelled saline
- the intensity of radiolabelled saline

The AUCs will be evaluated for each subsite and compared between treatments (A-D). Between-treatment differences in AUCs will be tested by means of one-way analysis of covariance (ANCOVA) with application method as a factor and the value at  $T_0$  as

covariate. Pair-wise comparisons will be made between each of the pulsed application methods and the continuous application (no pulse).

[figure not shown]

Figure 7. Example of superposition of anterior gamma camera images of radiolabelled aerosol after nasal delivery [9]. After deletion of the activity in the central nasal cavity, the aerosol penetration into the sinuses will be highlighted in B and D.

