### 2.3 Rational for current study

The proposed study aims to investigate the regional deposition in the nasal cavity of aerosols generated from the clinical NMN prototype using different pulse frequency modes. Information from this study will be used to aid in determining the optimal

deposition settings for future targeting of medication to the sinuses and within the nasal cavity.

Once beyond the nasal valve, the deposition pattern within the nasal cavity is vitally important. Deposition on middle meatus is of particular significance as this is the location of the ostiomeatal complex, a group of structures that receive drainage from the anterior and medial ethmoid cells, the frontal sinus and the maxillary sinus. Other important sites include the ostia of the sphenoid and posterior ethmoid sinuses, which are located superoposteriorly to the ostiomeatal complex on the sphenoethmoid recess and superior/supreme meatus, respectively. Improving the deposition to these regions is of clinical importance as it would translate into improved therapeutic effects in CRS, including patients that have undergone Functional Endoscopic Sinus Surgery (FESS).

To evaluate this, radio-labelled aerosols of a saline solution will be delivered using the clinical NMN prototype and sequential imaging will be performed using Single-photon emission computed tomography (SPECT) or positron emission tomography (PET) (depending on accessibility and availability of equipment in the hospital) and gamma scintigraphy imaging. Simultaneously, high resolution computed tomography (CT) scans of the nasal and sinus anatomy will be obtained from all participants and used as templates for overlaying subsequent deposition data to provide a detailed assessment of deposition characteristics.

Four different pulse frequency settings will be evaluated including: A) no pulse frequency (continuous delivery mode), B) a 10 Hz pulse frequency C) a 50 Hz pulse frequency and D) a 100 Hz pulse frequency based on preliminary *in vitro* studies and those investigated by other researchers [9].

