### 6.3.3 SPECT/PET Imaging

The imaging protocol commences immediately after the inhaled radiolabelled aerosol is administered. The following images are performed:

1. Planar imaging (anterior/posterior) of head and upper respiratory tract with participants sitting in front of the gamma camera head.
2. Dynamic SPECT or PET imaging of the head is performed with participants in the supine position for the first 20 minutes
3. Final repeat head SPECT or PET scan at 1 hour.

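### Percent clearance, retention and SPECT-based deposition are scaled to a seated planar total with no cross-calibration, and a PET option is offered that the 99mTc tracer cannot use

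*Protocol*

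**What the plan says.** Section 3.4 (Interpretation and assumption of quantitative data) sets the scale for all three quantities: "The quantitative assessment of nasal deposition, retention and clearance will be determined as a percentage of total nasal deposition". That total is "quantified using the first planar image immediately after inhalation of the radioaerosol". Clearance is the decrement between T0, T20 and T60; retention is an AUC from T0 to T60, analysed with the T0 value as covariate. The stated count corrections are background activity and radioactive decay.

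Section 6.3.3 itemises three images in order. The first, and the only planar one listed, is this: "Planar imaging (anterior/posterior) of head and upper respiratory tract with participants sitting in front of the gamma camera head". The next entry changes both mode and posture: "Dynamic SPECT or PET imaging of the head is performed with participants in the supine position for the first 20 minutes". The list then closes with a late image for which no posture is given: "Final repeat head SPECT or PET scan at 1 hour".

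The opening of Section 3.4 describes the acquisition differently. The planar image is taken "in front of a single-head gamma camera using the NMN device to capture a planar images", and then: "Subsequently, serial images (2 frames per second) will be recorded from the anterior and lateral view using the SPECT/CT". Section 2.3 leaves the choice between SPECT and PET open, "depending on accessibility and availability of equipment in the hospital". Section 6.3.1 names one radiolabel, 99mTc-DTPA.

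**The concern.** A planar count and a SPECT count of the same activity are generally not equal: sensitivity, attenuation, geometry and here posture all differ. A ratio or difference of the two is interpretable only if they have been calibrated against each other or come from the same series. The protocol states neither. It also does not say whether the T0 entering the clearance decrement is the planar image or the first dynamic frame, and the two choices push the result in opposite directions.

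At stake are the absolute size of clearance (the second secondary objective in Section 3.3), retention of intensity, and any sinus share read from SPECT and set beside the 6.5% benchmark or the >6% aim under Statistical consideration.

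Separately, Section 2.3 itself expands SPECT as single-photon and PET as positron-emission imaging. 99mTc is a single-photon emitter, so the PET option cannot be carried out with the tracer that the protocol specifies.

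**Working it through.** The protocol gives no figure for this point, so there is none to reproduce. The check traces the source of each count and then shows how sensitive the percentages are.

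**Source of each count, following Section 6.3.3**

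| Quantity | Mode | Posture |
|---|---|---|
| Total nasal deposition (denominator) | Planar | Sitting |
| T0 in the decrement | Not stated: planar or first dynamic frame | Sitting or supine |
| T20 | Dynamic SPECT or PET | Supine |
| T60 | SPECT or PET | Not stated; supine implied by the word repeat |

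**What the stated corrections do.** With the 6-hour half-life in Section 4.2, the activity remaining after decay alone is 0.5^(20/360) = 0.962 at 20 minutes and 0.5^(60/360) = 0.891 at 60 minutes. Decay correction restores these factors. It does nothing about a difference in count efficiency between modes.

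**Sensitivity.** Let c be true clearance and k the ratio of SPECT to planar count efficiency. The documents give no value for either; c = 0.30 and k = 0.8 to 1.2 are assumptions for illustration.

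- Reading 1, T0 planar and later values SPECT: apparent clearance = 1 − k(1 − c).
- Reading 2, T0 and later values all SPECT, only the denominator planar: apparent clearance = k × c.

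| k | Reading 1: 1 − 0.70k | Reading 2: 0.30k |
|---|---|---|
| 0.8 | 44% | 24% |
| 0.9 | 37% | 27% |
| 1.0 | 30% | 30% |
| 1.1 | 23% | 33% |
| 1.2 | 16% | 36% |

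The error changes sign between the readings, so even the direction of bias is unknown until the protocol says which image is T0.

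**Sinus share.** SPECT counts in the sinuses divided by a planar total give k times the true share. A true 6.5% reads 0.8 × 6.5 = 5.2% to 1.2 × 6.5 = 7.8%. It falls below 6% once k is under 6/6.5 = 0.923. A share formed as planar region over planar total has no k in it.

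**Between-frequency tests.** If k is the same for every participant and visit, both readings are linear transforms of the true percentage. A true difference d between two frequencies appears as kd, and its standard error is multiplied by the same k. F statistics and p-values for percent clearance are unchanged; only the reported size of the difference is stretched or shrunk.

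**After the change.** With baseline, later values and denominator from one series, k = 1 and both formulas return c.

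**The case against.** The strongest reply is that the protocol can be read consistently. Section 3.4 never says that the T0 of the decrement is planar, and dynamic SPECT over the first 20 minutes supplies an early tomographic frame. Section 6.1 mentions the gamma camera together with SPECT/PET imaging through to 1 hour, and Section 4.2 and Table 2 list gamma scintigraphy alongside SPECT or PET, so later planar images are not expressly excluded. Calibration detail may sit in the imaging procedures or the SAP. The main comparisons are also between frequencies within a participant, and the primary endpoint is an area.

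Much of this stands. It rules out presenting reading 1 as the only one, and it limits the harm to absolute values. It does not remove the point. Under reading 2 the denominator is still the planar total. The itemised list in Section 6.3.3 contains no later planar image, and a SAP cannot supply one that was not acquired. The cancellation depends on a constant k, which the protocol gives no basis for assuming.

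A reader might infer three stronger things that the documents do not support:

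- That the ethmoid and sphenoid sinuses (four of the eight named, counting left and right) cannot be measured at T0. No section confines regional T0 measurement to the anterior planar view. Section 2.3 plans overlay on CT, Section 3.4 mentions transaxial reconstruction and a lateral view, and Figure 7 is captioned as an example from a cited study.
- That a scanner change would be confounded with frequency. Treatment order is randomised (Sections 4.2 and 5.6), nothing in the text suggests changing SPECT cameras, and a usable switch to PET is not possible with 99mTc.
- That comparison with 6.5% is lost. A planar-over-planar share at T0 is internally consistent, and Figure 7, taken from the benchmark study, is captioned as anterior gamma camera images.

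**Conclusion.** The point holds for absolute percentages. Followed as written, percent clearance and retention, and any regional percentage taken from SPECT, mix planar and tomographic counts through an unstated factor. For a true clearance of 30% and assumed k of 0.8 to 1.2, the reported value could lie anywhere from 16% to 44% with a planar T0, or from 24% to 36% with a SPECT T0 and planar denominator. These ranges illustrate the sensitivity; they are not estimates of the actual error.

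It would go too far to conclude that the frequency comparison or the primary endpoint is invalid. A constant k largely cancels in the tests, and area in mm² does not use this denominator. The PET option is a separate, definite inconsistency with the sole tracer. Its basis is the physical nature of 99mTc together with the protocol's own expansion of the two abbreviations.

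**What to change.** - In Section 3.4, for clearance, retention and SPECT-based regional percentages, take the baseline (first dynamic SPECT frame), the 20-minute frame, the 60-minute scan and the total nasal denominator from the same SPECT series. State that the 0-minute value for clearance in Section 3.3 is that first frame.
- Require the same SPECT camera and acquisition settings at all four visits of a participant.
- Keep the immediate planar image. Use planar region over planar total at T0 for the comparison with the 6.5% benchmark.
- Delete the PET alternative wherever it appears (Sections 2.3, 4.2, 6.1 and 6.3.3, and Table 2).
- Reconcile the views and modes in Sections 3.4, 6.1 and 6.3.3: anterior and lateral serial images at 2 frames per second in one place, anterior/posterior planar followed by dynamic SPECT in another. State the posture at 1 hour.

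If the sponsor prefers to keep the planar denominator, the alternative is to state a planar-to-SPECT cross-calibration.

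The cost is wording, with no new scans. The downside is that the clearance baseline falls slightly after the end of administration, by the time needed to lie the participant down. The protocol does not give that delay, so the start time of the first SPECT frame should be recorded.

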Figure 2: (A) concept of final clinical device prototype (B) cumulative aerosol particle size distribution of PARI SINUS and other commercially available nebulisers vs. the NMN prototype. Purple and blue regions correspond to optimal particle sizes for lung and nasal deposition, respectively. ( $n=5 \pm \text{StDev}$ ).

**Preliminary study:** In-line laser diffraction studies, using the development-prototype NMN (Figure 2A), have shown that a narrow particle size can be achieved which is suitable for nasal drug delivery (Figure 2B). In general, the median particle diameter of isotonic saline after 3 seconds operation was  $53.9 \mu\text{m} \pm 2.6 \mu\text{m}$ . This is in comparison to  $2.75 \mu\text{m} \pm 0.15 \mu\text{m}$  for the PARI SINUS. Under these conditions, the output rate was 20x that of the PARI SINUS. Additionally, two other commercial nebulizers were tested (Omron® and AeroNeb-Go®) and it was shown that they were also not suitable for nasal deposition (Figure 2B). Subsequently, the effect of pulsation frequency (Hz) on aerosol generation and particle size using the NMN device has been investigated and shown that changing the pulse frequency had little effect on aerosol size, measured by laser diffraction (Figure 3A).

Using a commercially available silicon cast of the human upper respiratory tract (Koken LM005, Koken Ltd, Tokyo, Japan; also referred to in this study as ‘Boris’) (Figure 3B), the effects of pulsative frequency and orifice size of the mesh on nasal deposition were evaluated.

[figure not shown]

Figure 3: (A) Influence of pulse frequency at 10 and 50 Hz on aerosol particle size over a 3-second period.  $D_{0.9}$  represents diameter of 90th percentile cumulative size distribution. ( $n=5 \pm StDev$ ). (B) Assembly (left) and testing of prototype NMN (right) in nasal cast model. Yellow water sensitive coating reacts with saline and turns red upon contact. The circled region in top view highlights the maxillary sinus inlet.

Preliminary studies using the Boris model (Figure 4) indicated these particles were deposited within the nasal cavity, with no observable oral-pharynx deposition. It also demonstrated that by applying different pulsative frequencies different nasal deposition profiles could be achieved but these observations need to be confirmed *in vivo*.

[figure not shown]

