#### 3.2 Primary objective and endpoint

The main objective of the study is to determine the optimal frequency for the NMN that will provide the basis for future *in vivo* sinus targeting of drug delivery systems. The primary endpoint of this study is the total area of distribution (mm^2) of radiolabelled saline immediately after administration by the NMN (T0) in the different regions of the sinus cavity.

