### 4.2 Study design

This study will be performed in healthy Caucasian male participants with no history of sinusitis or chronic respiratory diseases.

Informed consent will be obtained for participants prior to the initiation of any study-specific procedures including screening. All participants will receive a head CT scan on their first visit.

The treatment sequence for the study participants will then be randomly applied with at least a 72-hours washout period between treatments (Table 1). The potential carry-over effect of the applied radiolabel is considered negligible since Technetium has a half-life of 6 hours, consequently a 'rest' minimum period of 72 hours is considered sufficient between imaging study days.

*Table 1. Treatment types to applied in the proposed study*

Treatment	Device	Application method
A	NMN	No pulsing (continuous mode)
B	NMN	10 Hz pulse
C	NMN	50 Hz pulse
D	NMN	100 Hz pulse

Each participant will receive a radio-labelled saline dose of 2.0 mL per visit by one of the application methods (Table 1), the order of which will have been randomly selected.

Nasal deposition, retention and clearance of radiolabelled saline solution will be measured using serial imaging of SPECT/PET and gamma scintigraphy. The study does not involve the use of novel treatments and is restricted to investigating the ability of the NMN device to target the paranasal sinuses.

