### 5.3.2 Exclusion criteria

Exclusion criteria are:

- Significant upper and lower respiratory infection within the previous 4 weeks
- History of chronic sinusitis or rhinitis
- History of recurrent lung infections.
- History of chronic lung diseases
- History of severe or multiple allergies, including hay-fever and perennial rhinitis
- History of nasal fracture, nasal deformities or nasal polyps
- History of disease, surgery, or abnormality of the upper respiratory tract, especially the nasal cavity.
- History of significant nose bleeds
- Participants using topical nasal medication e.g. decongestant, within the last 14 days of the first study day
- Participants unable to perform pulmonary function test according to ATS/ERS criteria
- Participants with documented or suspected, clinically significant alcohol or drug abuse
- Current malignant or cardiovascular disease
- Any serious or active medical or psychiatric illness
- Current smokers, i.e. those who had smoked within the last 12 months and 6 hours prior to the scan. A negative Cotinine test must be demonstrated at each visit.
- Participants who have any non-removable metal objects such as pacemakers, insulin/infusion pumps, cochlear and ear implant, metal plates, screws etc. in their head, neck, chest or abdominal area that may interfere with the /PET/SPECT/CT.
- Nasal jewellery or nasal piercing
- Participants with tattoos or permanent makeup above shoulder
- Participants for whom participation in this study will exceed the limit of total radiation exposure allowed in any 12 months period (5 mSv), or will exceed 10 mSv over the last five-year period [19].

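### The primary analysis names subsites that do not match the primary endpoint: surgically expanded ostia, which no eligible participant can have, and the oropharynx, which is not a sinus region

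*Protocol*

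**What the plan says.** Section 3.2 sets the primary endpoint as the total area of distribution of radiolabelled saline, in mm², immediately after administration, "in the different regions of the sinus cavity".

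Section 3.4, under the heading on interpretation of quantitative data, repeats the endpoint and says that it will be "evaluated for each of subsites (surgically expanded ostia of the paranasal sinuses and oropharynx". The one-way ANOVA on application method is then run at each subsite. Each of the three pulsed modes is compared with continuous delivery, two-tailed at 0.05. The clearance analysis and the two AUC retention analyses in the same section are also done for each subsite.

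On eligibility, section 4.2 states: "This study will be performed in healthy Caucasian male participants with no history of sinusitis or chronic respiratory diseases". Section 5.3.2 excludes participants with "History of disease, surgery, or abnormality of the upper respiratory tract, especially the nasal cavity".

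Two other descriptions of the regions stand in section 3.4. The quantitative assessment, expressed as a percentage of total nasal deposition by intensity, covers areas of the nasal cavity and "left and right of the maxillary, frontal, ethmoidal and sphenoidal sinuses using standard protocol". The regions of interest are said to be those of Figures 6 and 7, and the Figure 6 caption reads "Regions of interest of the nasal cavity of the right and left maxillary and frontal sinuses (MR, FR, FL and ML".

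**The concern.** The sentence that fixes where the primary endpoint is tested does not fit the endpoint or the population. One of its two subsites presupposes sinus surgery, which the eligibility criteria rule out. The other lies outside the sinus cavity. An analyst who follows the text cannot produce the endpoint of section 3.2. One who departs from it must choose the regions without guidance.

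That choice matters. Section 5.7 makes the study open-label for pulse frequency, the hypothesis in section 3.1 concerns deposition within the sinuses, and section 2.3 intends the results to support registration of the device. If the regions are settled only once the images exist, they can be settled with the treatment known.

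**Working it through.** No sample size, power or alpha figure depends on this point, so there is no plan figure to reproduce. The check sets the passages side by side.

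**1. Can the first subsite exist?** Section 5.3.2 excludes a history of surgery of the upper respiratory tract. The protocol counts the sinuses as part of that tract: the model of the upper respiratory tract in section 3.3 is one that "includes the sinus cavities (maxillary, frontal, ethmoidal, sphenoidal". Sinus surgery therefore falls under the exclusion. Section 4.3 plans for 11 completers, and 0 of 11 can have a surgically expanded ostium. Operated sinuses are otherwise mentioned only in section 2.3, as a group of patients who might benefit later.

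**2. Is the second subsite a region of the sinus cavity?** Section 3.3 lists the sinus cavities as maxillary, frontal, ethmoidal and sphenoidal. The oropharynx is not among them, nor in the intensity list, nor in the Figure 6 caption. Section 2.2 treats it as a site apart when it reports that particles were "deposited within the nasal cavity, with no observable oral-pharynx deposition".

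**3. Does another list settle the matter?**

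| Place in protocol | Measure | Regions named | Count |
|---|---|---|---|
| 3.2 | Area, mm² (primary) | Regions of the sinus cavity | Not listed |
| 3.4, primary analysis | Area, mm² (primary) | Surgically expanded ostia; oropharynx | None that fits 3.2 |
| 3.4, quantitative assessment | Percentage of nasal deposition by intensity | 4 sinuses × 2 sides, plus nasal cavity areas | 8 sinus regions |
| 3.4, Figure 6 caption | Regions of interest | 2 sinuses × 2 sides | 4 sinus regions |

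The eight-region list belongs to a different measure. The Figure 6 caption omits the ethmoidal and sphenoidal sinuses. Only the faulty parenthesis assigns named regions to the area analysis.

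**4. What turns on the choice?** There are 3 pairwise comparisons per region. Four regions give 3 × 4 = 12 primary pairwise tests, and eight give 3 × 8 = 24. The protocol does not say which set applies or whether one region or a total is primary.

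**5. How far does it reach?** Clearance and both AUC measures (area and intensity) refer to the same subsites and carry the same defect.

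**The case against.** The strongest reply is that the intent is plain. Section 3.2, which formally defines the endpoint, places it in the sinuses. Section 3.4 superimposes regions of interest of the nasal airways and sinuses on all serial images and takes the activity from them. The study calls itself exploratory, and the wording can be corrected before analysis with no data lost. All of this stands. A reader might infer from the parenthesis that the trial cannot answer its own question. The documents do not support that, because the sinuses will be imaged and quantified whatever the parenthesis says.

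A reader might also infer that the oropharynx is the only measurable subsite left. That goes too far. The parenthesis does refer to the paranasal sinuses through their ostia, and section 2.3 treats ostia as important deposition sites in their own right. Dropping the words about surgery would leave sites that the participants have. Ostia would still not be the sinus regions of section 3.2, so the two sections would still need to be reconciled.

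Third, the text could be taken to count more saline in the oropharynx as a benefit. It does not: the pairwise tests are two-tailed and no direction is stated. Measuring the oropharynx is legitimate. The fault is that it is listed as a subsite of the primary endpoint without being marked as a different kind of measure.

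The statistical analysis plan is not at hand and may name the regions. That would not cure the protocol, which does not leave the subsites open but states them wrongly. A plan faithful to section 3.4 would repeat the error, and one that used sinus regions would contradict it.

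**Conclusion.** The contradiction is real and should be corrected before any image is analysed. Of the two subsites given for the primary analysis, one has 0 evaluable participants out of 11 and the other lies outside the endpoint's definition. The alternative lists differ by a factor of two (eight sinus regions against four), so context does not settle which regions were meant.

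The consequence is limited to this: the regions for the primary test, and for clearance and retention, are contradictory and open to choice after the images are seen. The data to be collected are not at fault.

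The conclusion rests on reading the surgery exclusion as covering the sinuses, as the protocol's own usage indicates, and on the Figure 6 caption, since the images in Figures 6 and 7 are not shown.

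**What to change.** - In section 3.4, replace the parenthesis with the sinus regions meant in section 3.2, for example the left and right maxillary, frontal, ethmoidal and sphenoidal sinuses.
- Make the regions of interest in Figures 6 and 7 match that list, and use the same list for area, intensity, clearance and AUC.
- State before analysis which region or total is primary. A sum over the sinus regions is one option. The documents do not require it, and the sponsor may prespecify another.
- Report the oropharynx separately as off-target deposition, outside the primary endpoint.

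The cost is a wording amendment. The CT scan is already planned as a template for overlaying the deposition data, so no new visit, scan or participant is needed. If the ethmoidal and sphenoidal sinuses are kept, their regions of interest must be defined, because the Figure 6 caption does not include them.
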